### I.c. Rationale & potential benefits

Our proposal seeks to test a sleep timing intervention, proven to be successful in the laboratory, in a Field Trial in older night-shift workers, to improve their sleep thereby improving their alertness and performance on the night shift. This intervention is based on a strong scientific premise and the fundamental principles of circadian physiology and homeostatic sleep-wake regulation, and how these two sleep regulatory processes interact in humans. Studies by our group (58-61, 100, 101) and others (76, 102-110) have demonstrated that the length of prior wakefulness has a significant impact on alertness and performance, and that this impact is exacerbated during the biological night. The sleep schedule of our intervention was selected to minimize the duration (and therefore impact) of prior wakefulness before beginning the night shift.

The proposed translational field study is innovative, as relatively few controlled intervention field trials for sleep problems in older shift workers have been conducted (111). Previous interventions to improve performance or safety of shift workers in general (regardless of age) mostly focused on changing the shift schedule, controlling light exposure, and/or using behavioral, lifestyle or pharmacological aides to shift circadian timing, facilitate sleep, or enhance alertness (112). In real-life, work schedule changes or light exposure interventions are not always feasible from an organizational perspective, and therefore we focus on the individual older night worker and propose to test a sleep strategy as a home-based countermeasure to enhance sleep, thereby improving alertness and performance on night shifts. Furthermore, the proposed intervention does not lead to significant shifts of the circadian timing system, and thus is preferable for workers whose shift schedule rotates frequently and for those who adopt a night-sleep/day-wake schedule on days off. An intervention strategy that improves sleep, vigilance, and subjective sleepiness without shifting the underlying timing of the circadian system is thus preferable for night shift workers.

Prior interventions that focused on sleep used timed naps as a countermeasure to the alertness and 2018-P-002341 Detailed Protocol v5 2020\_09\_25

performance decrements associated with night work (113-116). Here, the innovative intervention we will field test is a long, consolidated sleep episode, typical of what most adult humans do when working days or evenings. We have found in our laboratory studies that older participants can adopt this schedule and when they do so, they have longer and less disrupted sleep. While our laboratory data suggest this approach is promising, we recognize that it may not be practical for all older shift workers. Therefore, in addition to testing the efficacy of the scheduled sleep intervention, we will investigate the acceptability of such a sleep strategy from older night workers' point of view through Focus Group discussions. In addition, it is important to evaluate the feasibility (barriers and facilitators) for adopting such a sleep strategy from the older night workers' perspective, which we will do through a Shift Worker Survey given to a large and diverse group of older shift workers. Together, the information from the proposed rigorous studies will be useful in developing specific recommendations for older night workers in general, and will allow us to maximize our ability to disseminate information about the intervention to a targeted audience and implement this in the real world of night workers.

## II. SPECIFIC AIMS

Working at night or on a rotating schedule can lead to misalignment between the timing of the biological clock and the work/sleep schedule, resulting in sleepiness, inattention, and impaired performance during the night shift and poor quality, shortened sleep during the day. These adverse effects of night work are worse in older workers compared to young workers, mainly due to their decreased ability to sleep during the day.

Most interventions focus on strategies to shift the timing of the biological clock (light therapy, light-blocking glasses during morning commutes, melatonin), and/or acutely increase alertness during work (enhanced lighting, caffeine or other stimulants, exercise). What is overlooked with these strategies is that night workers typically sleep in the morning, shortly after completing work. In doing so, they typically arise 8 or more hours prior to their next night shift, unlike most day workers who arise only an hour or two prior to beginning day work. Thus, night shift workers are not only attempting to work when their biological clock is promoting sleep, they begin work with a much greater sleep pressure due to prolonged wakefulness. Furthermore, they need to sleep when their biological clock is promoting wakefulness, causing sleep difficulties.

In simulated laboratory-based night work studies in older subjects carried out in the previously, we tested a strategy focused on sleep timing: scheduling the major sleep episode to begin in the early afternoon and extend into the evening, such that the worker awakens 1-2 h prior to their next night shift. We found that older participants were able to spend 8 h in bed in the afternoon-evening, they had significantly longer and less disrupted sleep than participants who slept *ad lib*, their on-shift alertness and performance during night shifts was increased, and they showed reduced levels of the stress hormone cortisol.

Whether this sleep timing intervention works in actual older night workers, as opposed to participants in lab studies, remains to be tested. We therefore will field test, in older night workers (age 50-65 years), the sleep timing intervention that we have developed in laboratory studies; we will examine the **efficacy** of this intervention in improving sleep duration and quality, as well as performance and alertness across 3 night shifts. We will also conduct a survey study among a large group of older shift workers to examine the factors that influence their ability to adopt such a schedule. Finally, we will have participants from both studies take part in focus groups where the **feasibility** and **acceptability** of the afternoon-evening sleep intervention will be examined. To evaluate the efficacy, feasibility, and acceptability of an 8-h afternoon-evening sleep schedule in the field/real world, our study will address the following Aims:

1. Test the hypothesis that older night shift workers scheduled to an 8-h afternoon-evening sleep episode will sleep longer and have fewer sleep interruptions than those randomized to an *ad lib* sleep/control condition.
2. Test the hypothesis that older night shift workers scheduled to an 8-h afternoon-evening sleep episode will show greater subjective and objective alertness on night shifts compared to those randomized to an *ad lib* sleep/control condition.
  - 2a. Conduct exploratory analyses to examine whether older night workers scheduled to an 8-h afternoon-evening sleep episode show reduced physiological stress (cortisol), reduced subjective stress and fatigue, and improved mood and quality of life compared to those randomized to an *ad lib* sleep/control condition.
  - 2b. Conduct exploratory analyses to compare an 8-h afternoon-evening sleep schedule to an 8-h free sleep

schedule in older night shift workers for impacts on sleep duration and quality, alertness and performance, stress, subjective fatigue, mood, and quality of life, to evaluate the effect of the timing of sleep regardless of duration. 3. Test how individual factors influence the ability to adopt an 8-h sleep episode while working night shifts. In a shift worker survey, we will determine the percentage of night shift workers who report their ability to adopt an 8-h sleep schedule (regardless of timing), those who report being able to adopt an 8-h afternoon-evening sleep episode, and we will then examine how demographic (e.g., sex) and other factors (e.g., occupation) impact this adoptability in order to evaluate the *feasibility* of an 8-h afternoon-evening sleep schedule for older night workers. In debriefing focus groups, we will examine participants' perceptions of their ability to adhere to an 8-h afternoon-evening sleep schedule (*acceptability*), barriers to following such a schedule, and their willingness to adopt such a schedule outside the study for future prolonged implementation.

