### I.b. Preliminary Studies

In our preliminary laboratory study we evaluated a sleep and circadian based treatment to adapt older adults to a night shift schedule (4), as we found to be successful in a previous laboratory study in young adults (80). The combined treatment of scheduled afternoon-evening sleep and enhanced lighting increased sleep duration and partially aligned circadian phase with sleep and work timing, resulting in improved night shift alertness and performance in older adults. As a follow-up study (6) to the studies described above (4, 80), we also carried out a study to examine the contribution of scheduled afternoon-evening sleep by itself, to test whether the timing of the sleep episode or the duration of time-in-bed could improve sleep duration when working nights. Compared to the control group, the fixed 8h afternoon-evening sleep group had significantly longer time-in-bed and total sleep time, and greater mean sleep efficiency following night shifts. These preliminary data indicate that older adults can comply with an 8h scheduled afternoon-evening sleep episode after night shifts, and in doing so, they are able to obtain more sleep. We also found that the plasma cortisol levels were significantly reduced in the combined treatment group and evening sleep group compared with the control group, suggesting that the sleep intervention groups were **less stressed** than the *ad lib* sleep group. If this is the case, it may indicate that the sleep intervention can have implications for improved health outcomes. To summarize, preliminary laboratory studies have shown that an afternoon-evening sleep intervention before night work improves sleep duration, night shift sleepiness and vigilance, and cortisol independent of circadian phase shifts.

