The Intervention Block is similar to the Baseline Block, consisting of at least three consecutive 8-h night shifts, with the participants wearing an activity monitor, maintaining a daily sleep e-diary, and rating alertness, mood and attention three times per night shift using a mini iPad provided by the investigators. At the end of the first night shift, the participant will be told about their randomization group. In the control group (Group A), participants will not be given any instructions about the timing or duration of their sleep, but will be instructed to follow their usual night shift sleep routine. In the 8-h afternoon-evening sleep intervention group (Group B), participants will be instructed to go to bed between 13:00 and 14:00 (depending on their individual commute time) and to remain in bed attempting to sleep for 8 hours (until 21:00-22:00) before the next two night shifts. In the 8-h free sleep group (Group C), participants will be instructed to remain in bed for 8 continuous hours before the next two night shifts, but will not be given any instruction regarding which 8 hours they should sleep. Immediately following the last night shift, the participant will have the option to take a saliva sample to measure their stress level (cortisol), and they will complete a follow-up questionnaire where their fatigue, recovery, stress, and quality of life will be reassessed to investigate any exploratory short-term changes resulting from the intervention schedule. After completion of the two blocks, the participant will send back the activity monitor and iPad in a prepaid secured return package by mail or an investigator will arrange to meet with the participant to retrieve the activity monitor, iPad, and cortisol sample. Within 3 months after completion of the study blocks the participant will be invited to take part in a virtual Focus Group by secure videoconferencing (via HIPAA-compliant & MGB-approved Zoom).

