#### **VI.d. Power analysis**

For the Field Trial we plan to enroll up to 100 participants, with at least 25 participants per group for three groups including A) control group (ad lib sleep); B) 8-h afternoon-evening sleep timing group; C) 8-h free sleep group. For the Shift Worker Survey, we aim to enroll up to 1,000 participants. In the Focus Groups we plan to enroll up to 60 participants, ~30 participants who complete the Field Trial and ~30 participants who complete the Shift Worker Survey.

Our sample size calculations for the Field Trial are based on the preliminary data from our laboratory study (6) comparing the ad lib sleep group with the 8-h scheduled afternoon-evening sleep group, and using total sleep time (TST) and Fragmentation Index (FI) after 2 nights as the outcome measures of interest. For TST, 25 participants per group will give us the power to detect a difference of as few as 78 minutes between groups ( $\alpha=0.05$ ,  $\beta=0.9$ , assumed  $\sigma=84.4$  min), a difference much smaller than that observed in our preliminary study ( $221.4 \pm 84.4$  vs.  $403 \pm 58.5$  min). For FI, 25 participants per group will give us the power to detect a difference of 37 in the fragmentation index (assumed  $\alpha=0.05$ ,  $\beta=0.9$ , assumed  $\sigma=39.9$ ), a smaller difference than that observed in our preliminary study ( $73.3 \pm 39.6$  vs.  $35.2 \pm 20.03$ ).

Our sample size calculations for the Shift Worker Survey are based on multivariable analysis. With at least 500 participants, we will have 90% power to detect an odds ratio of 1.51 for any continuous factor with one standard deviation difference, or 2.10 for any binary factor (yes vs. no) with a two-sized z-test at alpha=0.05 level, assuming the variance explained by other factors in the same model is 0.2.

Our sample size of 30 participants for the Focus Groups were selected to solicit qualitative information from approximately half of the Field Trial participants who were randomized to a sleep intervention, and from approximately 10% of the Shift Worker Survey participants who report being unable to adopt an 8-h sleep schedule when working night shifts.

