### **VIII. b. Potential Benefits to society**

Night and rotating shift work can result in shortened and disrupted sleeping during the daytime, leading to sleepiness on the following night shift and an increased risk of accidents both at work and while commuting home. While the sleep intervention we will test may appear so simplistic as to not merit testing, the facts are that most shift workers do not devote sufficient time for sleep. A rigorous field study testing whether remaining in bed attempting to sleep will result in longer and higher quality sleep could serve as important evidence that a 2018-P-002341 *Detailed Protocol v5 2020\_09\_25*

behavioural strategy could improve sleep quality for many shift workers. Evidence supportive of this strategy will also provide guidance for individual shift workers, employee health and wellness programs, and fatigue management plans. A practical nonpharmacologic treatment for improving the sleep of older night workers holds great potential in providing a specific and sustainable countermeasure that would enhance alertness, mood, safety, and general well-being and may result in longer-term health impacts.

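### Aims 1, 2 and 2a test the whole 8-h afternoon-evening schedule against usual sleep, so a positive result cannot by itself be credited to timing, and the plan commits to no as-randomised estimate of timing or of free-timed 8 h in bed

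*Combined protocol and SAP*

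**What the plan says.** **Aims (Section II).** Aim 1 is to "Test the hypothesis that older night shift workers scheduled to an 8-h afternoon-evening sleep episode will sleep longer and have fewer sleep interruptions" than participants randomised to ad lib sleep. Aim 2 (alertness) and Aim 2a (stress, fatigue, mood, quality of life) use the same two groups. Aim 2b is exploratory and compares the afternoon-evening group with the 8-h free sleep group, "to evaluate the effect of the timing of sleep regardless of duration". No aim names free sleep against ad lib.

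**Group instructions (Section V, Intervention Block).** Group A receives no instruction on when or how long to sleep. Group B is given a bedtime between 13:00 and 14:00 and 8 h in bed. In Group C, "participants will be instructed to remain in bed for 8 continuous hours before the next two night shifts", with the hours left to the participant.

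**How the intervention is described.** Section I.c opens: "Our proposal seeks to test a sleep timing intervention, proven to be successful in the laboratory". Section VIII.b instead presents the study as "testing whether remaining in bed attempting to sleep will result in longer and higher quality sleep". In the laboratory pilot (Section I.b), "the fixed 8h afternoon-evening sleep group had significantly longer time-in-bed and total sleep time", so the pilot comparison also mixed timing with time in bed.

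**Analysis (Section VI).** The Aim 1 model has a three-level group factor and says that groups will be compared, without listing contrasts. The Aim 2b paragraph says the comparison may be done. For it, Group C participants who chose afternoon-evening sleep are counted with Group B. Section VI.d bases the sample size on B against A only.

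**The concern.** B minus A contains two components: being told to stay in bed for 8 h, and being told which 8 h. If the gain came mostly from the first, Aims 1 and 2 would still be positive. With the intervention labelled as sleep timing and a rationale built on shorter wakefulness before the shift, such a result invites the conclusion that afternoon-evening timing works.

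Two randomised contrasts bear on this. B minus C asks what prescribing the hours adds when both groups have 8 h in bed. C minus A asks whether 8 h in bed at self-chosen hours beats usual sleep. The plan weakens the first and does not name the second. The second is the practical question for a worker who cannot sleep in the afternoon, and it is the randomised contrast closest to the description in Section VIII.b. The data for both will be collected in any case.

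**Working it through.** **1. Which instructions each contrast varies (Section V)**

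| Contrast | 8 h in bed instructed | Hours prescribed | Status in the plan |
|---|---|---|---|
| B minus A | differs | differs | Aims 1, 2, 2a |
| B minus C | same | differs | Aim 2b: exploratory, optional, regrouped |
| C minus A | differs | same (neither) | not named; estimable from the three-level factor |

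Since B − A = (B − C) + (C − A), a positive B − A does not show which part produced it.

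**2. Reproducing the plan's figure (Section VI.d).** The plan says: "For TST, 25 participants per group will give us the power to detect a difference of as few as 78 minutes between groups". Inputs: difference 78 min, SD 84.4 min, alpha 0.05, and a printed beta of 0.9 that must mean power 0.90. Sidedness is not stated; two-sided is assumed because it reproduces 25 per group (one-sided gives 21).

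n per group = 2 × SD² × (1.960 + 1.282)² / difference² = 2 × 84.4² × 10.51 / 78² = 24.6, so 25.

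The figure reproduces. Power at 25 per group is 0.904 by the normal approximation and 0.893 by the t-test. It applies to B against A only.

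**3. Precision of any pairwise difference in total sleep time (TST).** SE = SD × √(2/n), with n = 25.

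- SD 84.4 (ad lib arm of the pilot, used by the plan): SE = 84.4 × √(2/25) = 23.9 min, 95% CI about ± 48 min.
- SD 58.5 (scheduled arm of the pilot, the only scheduled-sleep SD printed; its use for Group C is an assumption): SE = 58.5 × √(2/25) = 16.5 min.

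**4. Power for B against C** (two-sided t-test, alpha 0.05, 25 per group, noncentrality = difference / SE). The pilot difference is 403 − 221.4 = 181.6 min. How much of any B − A difference is due to timing is not in the documents, so the timing component is varied.

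| Timing component | Power, SD 84.4 | Power, SD 58.5 |
|---|---|---|
| 20 min | 0.13 | 0.22 |
| 40 min | 0.375 | 0.66 |
| 45.4 min (25% of 181.6) | 0.46 | 0.77 |
| 90.8 min (50% of 181.6) | 0.96 | >0.99 |

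At 33 per group (100 completers in three groups), power for 40 min is 0.475 at SD 84.4 and 0.78 at SD 58.5.

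**5. Limiting case.** If all of a 78-min B − A difference came from time in bed, Aim 1 would still reach significance with probability 0.89 at SD 84.4, and B against C only at the 5% error rate. If 78 min split equally (78 / 2 = 39 min each), each component would have power 0.36 and need about 100 per group for 0.90.

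**6. Effect of the regrouping.** Suppose 5, 10 or 15 of the 25 Group C participants are moved to B (assumed; the plan gives no expected number). At SD 84.4, the difference detectable with power 0.90 rises from 79 min to 81, 86 or 99 min. The larger problem is not numerical. The moved participants chose their hours after randomisation, so the groups then differ by self-selection as well as by assignment.

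**The case against.** The plan saw the confound. It randomised Group C, and Aim 2b exists to separate timing from duration. B minus C, not C minus A, is the contrast for timing, so leaving C minus A out of the aims does not by itself cause misattribution. The hypotheses of Aims 1 and 2 are worded for an 8-h afternoon-evening episode, and B against A is a valid randomised test of that schedule. The Aim 1 model carries all three groups, so C minus A is not excluded. All of this stands.

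A reader might infer that a gain from time in bed alone would be reported as success of sleep timing. The documents do not support that: nothing says Aim 1 will be interpreted without Aim 2b. A reader might also infer that Aim 2b is bound to be too imprecise. That holds near the 78 min the plan powered for, at the ad lib SD. It does not hold if something like the pilot's 181.6 min recurs and half is due to timing. The t-test figures also ignore the repeated nights and baseline in the planned mixed model, which may reduce the SE; the correlation needed to show this is not given.

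The regrouping has a rationale too. If many Group C participants choose the afternoon, as-randomised B minus C understates the effect of the hours actually slept. That supports showing the regrouped result as well, not relying on it alone.

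What the objection leaves untouched is that the only timing contrast is optional, unpowered and not as randomised, and that no text commits to C minus A or says how B minus A is to be read beside the other two.

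**Conclusion.** The point holds as a matter of prespecification and interpretation, not as an error in arithmetic or a flaw that invalidates Aims 1 and 2. A positive B minus A supports the whole schedule. As written, the plan commits to no as-randomised estimate of what prescribed timing adds, and names none of what 8 h in bed at free hours achieves against control.

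The size of the problem depends on the unknown timing component and on the SD. Power for as-randomised B against C at 25 per group runs from 0.13 (20 min, SD 84.4) to 0.96 or more (90.8 min). For 40 min it is 0.375 or 0.66 according to the SD. Over the lower part of that range a non-significant B minus C would say little. The case for naming the contrasts does not depend on the split. Assumptions: two-sided tests, equal allocation, one TST value per participant, and a common SD in the two groups compared.

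**What to change.** In Section II and in the Aim 1, Aim 2 and Aim 2b paragraphs of Section VI:

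- Commit to reporting, from the same mixed model, the as-randomised B minus A, B minus C and C minus A differences on Intervention nights 2 and 3, each with a 95% CI.
- Name C minus A as a secondary contrast.
- Keep any regrouped B against C analysis as supplementary, labelled as not randomised.
- State that B minus A is the effect of the whole schedule (8 h in bed plus fixed hours), that benefit is credited to timing only as far as as-randomised B minus C supports it, and that a non-significant B minus C is not evidence that timing does not matter.

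The cost is a few lines of text, with no new data, visits or participants and no change to what any group is asked to do. The downside is one more secondary contrast and a possibly narrower claim about timing. The change should be made before the data are analysed, because much of Section VI is worded as what may be done.
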